**Table 5. Power Analyses**

Time/Test	PN plus DVD (n=115 at 9 mos)	DVD only (n=115 at 9 mos)	Usual Care (n=115 at 9 mos)	Power
9 month/ Any Test	44%	20%	5%	.80-.99

group). By 12 months, the 150 in each intervention group will decrease to 115 through an approximate 25% attrition. The multivariable logistic regression models for the intervention effect on the CRC screening completion outcome while accounting for covariates will very likely have greater than 80% power, more than for the bivariate models because a smaller sample size is required when

covariates are added to the model. In addition, this sample size will most likely ensure greater than 80% power for other outcomes of Aim 1 (quality of bowel preparation, anxiety, and satisfaction) because they are continuous or ordinal variables. Specifically, the analysis of continuous outcomes using a general linear model will have 99% power to detect a

small effect size of .50 standard deviation units between outcome means, and the ordinal logistic regression models will have more information than the binary models.

For Aim 2, our main interest is in whether the intervention effects differ by age, race, gender, and income. We consider this aim to be exploratory as we do not have preliminary data to estimate the effect sizes; however, we feel it is important to explore interactions in this study as they may identify subgroups of patients who may not need the more intensive support of a PN. For Aim 3, the revised sample size of 115 per group will allow for the detection of mediation effects with 80% power assuming the effect sizes from the intervention to mediator and from the mediator to outcome are moderate or higher (which is what is typically assumed in a power calculation). For Aim 3, to test mediation effects, we will use the percentile bootstrap method to estimate the indirect/mediated effect. Simulations of the two-path mediation model in Mplus (Table 2) show that 115 subjects per group are needed to have 80% power to test the total indirect effect using the Sobel approach when the effect of the independent variable (the intervention variable here) on the mediator is small (.2) and independent variable on outcome is medium (.39). Using the percentile bootstrap method instead of Sobel should afford the same or greater power.

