**Aim 2. Examine age, race/ethnicity, sex and income as potential moderators of intervention effects. (RQ-4, HT-1, HT-2, HT-3, HT-4)** We will fit multivariable models as in Aim 1, except now including interaction terms for age (< 65, age 65+), race/ethnicity (Non-hispanic Black, Non-hispanic White), sex (male, female), and annual income (<\$15,000, ≥\$15,000), respectively. Moderators will be identified by significant interaction terms in regression models. The key moderation effects of interest will be between PN+DVD vs. DVD only. Moderation of PN+DVD vs. usual care, and DVD only vs. usual care also will be examined. Hispanics will be excluded from race/ethnicity interaction tests due to small sample sizes.

**Aim 3. Examine changes in knowledge and health beliefs (knowledge, perceived risk, perceived benefits, barriers, and self-efficacy) as potential mediators of intervention effects. (RQ-6)** Mediation analysis will be conducted to identify potential mediators. Specifically, for each of the variables (changes in knowledge, perceived risk, perceived benefits, perceived barriers, and self-efficacy) mediation effects will be estimated in an logistic regression setting, fitting the appropriate mediation models using MPlus and then testing indirect effects using the percentile bootstrap approach to estimate the indirect effect. We will fit models that estimate the effects of PN plus DVD vs usual care and DVD only vs usual care, and also models that compare the strength of the indirect effects between the PN plus DVD and DVD only arms. We expect to see a difference in mediation effects mainly on barriers, with the PN plus DVD having a greater mediation effect on barriers than DVD only.

**C.14. Potential problems, strategies and benchmarks for success.** Potential problems are described below along with plans to minimize them. (*IR-6, MD-1, MD-2, MD-4*)

- *Loss to follow-up:* It is anticipated that there will be some loss to follow-up because of participant dropout, death, or relocation. Based attrition data through May 31,2019 , we estimate the loss to be approximately 25% over the 9-month study period, which has been accounted for in the revised power analysis and sample size determination.
- *Limited internal validity:* Randomization will minimize the influence of extraneous variables on outcomes.

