**D. Potential Benefits of the Proposed Research to Subjects and Others.** Participants in intervention groups may benefit from the information and tangible assistance received to encourage them to complete a CRC screening test. Both groups will receive information about colorectal cancer, the benefits of CRC screening, and detailed instructions on completing the bowel preparation for those who undergo colonoscopy. If found to be effective, these interventions will directly benefit patients who, despite having received a recommendation for CRC screening from their provider, did not complete that test. These interventions have great potential to decrease both CRC incidence and mortality in a group that bears disproportionate burden from this disease. This study may also indirectly benefit all people by comparing two effective interventions that can be easily translated into practice in other clinical settings. Information gained from this study may be useful to researchers and health professionals who are interested in developing new interventions to increase CRC screening rates.

**E. Importance of the Knowledge to be Gained.** This study will contribute to knowledge by answering several important questions. CRC screening has the ability to not only detect cancer in early stages while it is most treatable, but also to prevent CRC through removal of precancerous polyps. However, these benefits are not realized if patients do not adhere to provider recommendations to be screened. This study will aid our understanding of interventions that can increase screening, thereby decreasing risk for development of - and death from - CRC. This comparative effectiveness study will contribute to knowledge about the impact of two promising health system interventions that have potential for translation into clinical practice. Importantly, enhancing our understanding of which subgroups of the study population are more likely to respond to the DVD intervention alone and which members may require more intensive, interpersonal interventions, such as PN, will allow us to intervene more appropriately and efficiently.

**F. Inclusion of Women and Minorities.** Both men and women will be included in the proposed study. The proposed study will enroll non-Hispanic Black, non-Hispanic White, and Hispanic patients to test two theory-based interventions, alone and combined, against usual care.

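### Aim 2 cuts age at 65 for its interaction test, which costs power for any graded age effect, and its rule for naming moderators sets no significance level for 12 tests

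*Combined protocol and SAP*

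**What the plan says.** Section C.13 sets this aim: "Examine age, race/ethnicity, sex and income as potential moderators of intervention effects". The models are those of Aim 1 with interaction terms added, and every moderator has two levels. Age is cut at 65 (the text begins "interaction terms for age (< 65, age 65" and closes the bracket after the upper group). Income is cut at $15,000. Race/ethnicity is non-Hispanic Black or White, and sex is male or female.

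The contrasts are ranked: "The key moderation effects of interest will be between PN+DVD vs. DVD only". The section then adds: "Moderation of PN+DVD vs. usual care, and DVD only vs. usual care also will be examined". The decision rule is "Moderators will be identified by significant interaction terms in regression models". Aim 2 in C.13 gives no significance level, multiplicity rule or limit on interpretation. The .017 level in C.12 and C.13 is set only for the Aim 1 pairwise tests.

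Section C.12 describes the status of the aim: "We consider this aim to be exploratory as we do not have preliminary data". Under Protection of Human Subjects, part E expects the trial to show "which subgroups of the study population are more likely to respond to the DVD intervention alone".

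On age itself, C.3 admits African American patients aged 45–75 and others aged 50–75. C.9 lists age among the demographic items. E.1 uses under 65 against 65 and over as a randomisation stratum. For Aim 1, C.13 already allows continuous individual characteristics in the models.

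**The concern.** Cutting a continuous variable in two discards the differences within each half. A patient of 51 and one of 64 are treated as the same age, and patients of 64 and 66 as different. If the benefit of adding the navigator changes gradually with age, the two-level test sees only part of that gradient. Aim 2 has no power calculation, so it has little information to give away.

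The second issue is the wording of the rule. Four moderators on three contrasts make 12 tests, and a significant term among them names a moderator. The reader is not told the level of each test or how many false positives to expect. The plan hopes to learn who may not need the navigator, so a chance finding stated as an identified moderator could be given more weight than it deserves.

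**Working it through.** **The plan's own figures.** The documents give no power or error rate for Aim 2, so there is none to reproduce. Table 4 concerns Aim 1 only. At 115 per arm and two-sided .05/3, the pooled normal formula with continuity correction gives 92.1%, over 99.9% and 80.8%, against 92%, 99% and 80% stated.

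**1. Loss from cutting age at 65**

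Inputs: the age limits come from C.3. The distribution of age within them is not given and is assumed. The interaction is assumed linear in age, with 80% power at two-sided .05 when age is continuous.

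The two-level test keeps a share r² of the information, where r is the correlation between age and its two-level version.

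- Uniform ages: r² = 3q(1−q), where q is the share aged 65 or over. For ages 45–75, q = 10/30 and r² = 0.667. For ages 50–75, q = 10/25 and r² = 0.72.
- Normal ages: r² = φ(z)²/[q(1−q)], where z is the normal quantile with share q above it. For q = 0.20, 0.2800²/0.16 = 0.490. For q = 0.25, 0.3178²/0.1875 = 0.539.

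Remaining power is Φ[(1.960 + 0.842)·r − 1.960].

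| Assumed ages | r² | (1.960 + 0.842)·r | Power left |
|---|---|---|---|
| Uniform 45–75 | 0.667 | 2.287 | 63% |
| Uniform 50–75 | 0.72 | 2.377 | 66% |
| Normal, 20% aged 65+ | 0.490 | 1.961 | 50% |
| Normal, 25% aged 65+ | 0.539 | 2.057 | 54% |

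The correlation is symmetric. If the true effect were a step exactly at 65 and it were tested with linear age, the same r² would apply in reverse.

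**2. False moderators under the rule**

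Inputs: four moderators and three contrasts (C.13). Alpha of .05 per test is assumed, because the section gives none. One outcome is counted, and the moderators are treated as independent of each other.

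- The four key contrasts alone: 1 − 0.95⁴ = 18.5%.
- All 12 tests, if independent: 1 − 0.95¹² = 46.0%.
- The three contrasts within a moderator are linearly dependent. The studentized range (three groups, infinite degrees of freedom, cut-off 1.96·√2 = 2.772) gives 12.2% per moderator. Over four moderators, 1 − (1 − 0.1223)⁴ = 40.6%.
- At .05/3 per test, the same steps give 4.4% per moderator and 16.5% over four.

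These are large-sample figures. Logistic interaction models were also simulated with no true interaction, at 115–150 per arm. Moderator prevalences were assumed at 25%, 35%, 59% and 50%; Table 6 guided the 35% and 59%. The table shows the chance of at least one false moderator at .05 per test.

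| Screening rates (usual care / DVD / DVD plus navigator) | Wald | Likelihood ratio |
|---|---|---|
| 5/20/44% (C.12) | 25–28% | 47–48% |
| 18/26/44% (18% and 26% from the earlier trial in B.1) | about 40% | 43–44% |
| 20/20/20% | 38–40% | not run |

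The low Wald values reflect sparse usual-care events: 5% of 115 is about 6, before any split by moderator.

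**The case against.** **The cut has a design reason.** It is prespecified and matches a randomisation stratum, so the arms are balanced on it. That stands as a reason to show the two age groups. It does not require a two-level interaction term, since a stratified trial can model the same variable continuously.

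**The size of the loss rests on assumptions.** The documents give no age distribution and no evidence that an age effect would be graded. This stands, which is why the loss is given as a range and why a step at 65 is named as the case where continuous age does worse.

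**The same loss could be claimed for income.** A reader might infer it from the $15,000 cut. C.9 says only that income is assessed and gives no response format, so the documents do not show that finer information exists.

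**A 40% false-positive rate might be read as a property of the plan.** The documents do not support that. C.13 sets no alpha for these tests, and at .05/3 the figure would be about 16.5%. The plan also puts one contrast per moderator first, and those four tests carry 18.5% at .05.

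**The exploratory label might be read as contradicted by a rule on who receives navigation.** No such rule exists. C.12 says that interactions may identify subgroups. The dissemination section says that one trial rarely changes practice and that confirmation is needed. Unadjusted, prespecified interaction tests are a common choice for an exploratory aim. What remains is that the C.13 rule is worded more firmly than that status warrants.

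**Formal error control might seem the natural remedy.** One option is a joint 2-df test per moderator, Holm-adjusted over four, before the key contrast is examined. The first step would be at .05/4 = .0125. With equal arm variances, a key contrast with 80% power at .05 has noncentrality (1.960 + 0.842)² = 7.85. It would pass that step 51% of the time if the effect is symmetric between the two active arms, or 67% if it lies only in DVD plus navigator (noncentrality 4/3 × 7.85 = 10.47). That loss is similar to the loss from cutting age, so the gate is not recommended here.

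**Conclusion.** The point holds as a modest, inexpensive improvement. Cutting age at 65 would reduce 80% power for a graded age interaction to about 63–66% with uniform ages, or 50–54% with normal ages and 20–25% aged 65 or over. Both distributions are assumed, and the loss applies only if the effect changes roughly linearly with age.

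The rule for naming moderators is a secondary, wording-level point. At an assumed .05 per test, for one outcome and roughly independent moderators, the chance of at least one false moderator is about 40% over 12 tests (simulated 25–48%) and 18.5% over the four key contrasts. For an exploratory aim this calls for cautious reporting rather than strict family-wise control. Neither part touches the primary analysis.

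**What to change.** - In C.13, Aim 2, enter age as continuous in the arm-by-age interaction. Check linearity, for example with a spline, and report the arm contrasts at chosen ages. Keep the under-65 and 65-and-over table as description by randomisation stratum.
- Treat income the same way only if it was recorded in ordered bands. Check the baseline form first.
- Replace the rule that significant terms identify moderators. Report every interaction as an estimate with its interval, state the number of tests and the level used, label the results hypothesis-generating, and lead with DVD plus navigator against DVD alone.

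**Cost.** SAP wording and analysis code only, with no new data or participants. The price is a linearity assumption, which can be checked, and less power if the true age effect is a step at 65.

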**2. Examine age, race/ethnicity, sex, and income as potential moderators of intervention effects. (RQ-4)**

**3. Examine changes in knowledge and health beliefs (perceived risk, perceived benefits, perceived barriers, and self-efficacy) as potential mediators of intervention effects. (RQ-6)**

[figure not shown]
Both interventions can serve as adjuncts in any existing health care system to facilitate completion of CRC screening and improve the quality of bowel preparation. A number of complex factors may contribute to low CRC screening completion rates after provider referral, but more work is needed to understand these factors. We will explore whether the effects of these interventions differ for various subgroups of participants. Heterogeneity of treatment effects will be determined by examining age, sex, and race/ethnicity as potential moderators. **(HT-1)**

Figure 1. Conceptual Model Adapted from Warnecke, et al. 2008

**C.1. Conceptual Model.** The model guiding this study was adapted from Warnecke and colleagues (Figure 1). This multilevel model shows the proximal, intermediate, and distal determinants of health that will be targeted by the interventions. Consistent with this model, we will test a telephone-based patient navigation intervention that will provide social support (social relationships) and access to community resources (physical context) for people who have been scheduled for colonoscopy. Specifically, the patient navigators (PNs) will provide individualized support based on assessment of demographics, knowledge, health beliefs, and barriers. By interacting with the health care system and community resources, they will assist patients to overcome their unique logistical and other barriers to CRC screening. A tailored DVD titled “*Time to ACT: Approaches to Colon Testing*” will be designed to increase knowledge, health beliefs, and self-efficacy for CRC screening.

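### Aim 3 names change scores as mediators and specifies no baseline mediator score in either equation, so the mediator slope is unbiased only if change itself drives screening

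*Combined protocol and SAP*

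**What the plan says.** - **Aim (section C, Aim 3):** "Examine changes in knowledge and health beliefs (perceived risk, perceived benefits, perceived barriers, and self-efficacy) as potential mediators of intervention effects".
- **Analysis (section C.13, Aim 3):** for each of "changes in knowledge, perceived risk, perceived benefits, perceived barriers, and self-efficacy) mediation effects will be estimated in an logistic regression setting". Indirect effects are to be fitted in Mplus and tested by percentile bootstrap. No equation is written out. Table 3 collects knowledge and all the listed beliefs at T1 and T2 only, so a change can only mean T2 minus T1.
- **Covariates (section C.13):** baseline demographics that differ across groups at p < .20, and exposure variables (DVD viewing, number of navigator contacts). The Aim 1 models also take unspecified individual characteristics. No baseline belief or knowledge score is named.
- **Power (section C.12):** the claim is that "the revised sample size of 115 per group will allow for the detection of mediation effects with 80% power". A condition on the size of both paths is attached to it: "assuming the effect sizes from the intervention to mediator and from the mediator to outcome are moderate or higher". The supporting simulation is reported to give this result: "115 subjects per group are needed to have 80% power to test the total indirect effect using the Sobel approach". Its stated inputs are that the intervention's effect "on the mediator is small (.2) and independent variable on outcome is medium (.39"). On the switch of test, the section adds: "Using the percentile bootstrap method instead of Sobel should afford the same or greater power".

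**The concern.** Randomisation follows the baseline interview, so the arm can move only the T2 score. The indirect effect is therefore the arm effect on T2 multiplied by b1, the effect of the T2 score on screening, whatever the baseline effect b0 may be. A change score used alone forces the two effects to be equal and opposite. Suppose self-efficacy at follow-up is what matters. A participant who starts high and stays high then shows no change, yet is likely to be screened. The change score counts that person against the mediator, and the slope shrinks.

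Section B promises to show through what mechanisms the interventions work. A true mediator could be missed or reported at a fraction of its size, and two analysts following the same text could report indirect effects that differ about twofold.

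**Working it through.** **1. The plan's own 80%.** The inputs in C.12 are 115 per group (230 per contrast), a Sobel test, and values of .2 and .39. No alpha is given for Aim 3, so two-sided .05 is assumed. As worded, .39 runs from independent variable to outcome, so no mediator-to-outcome path is stated; here it is assumed to be that path. Simulated Sobel power for a linear outcome is then:

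- .2 per unit with arms coded ±1 (0.4 SD between arms): about 82%, or 84% fully standardised. This is near the stated figure, and 80% needs about 110–111 per group.
- .2 SD between arms (0/1 dummy coding, the coding C.13 gives for Aim 1): about 29%.

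The stated figure can be approached only on the first reading.

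**2. Slope from a change-only model.** Let screening depend on b1·M1 + b0·M0 (M1 = T2 score, M0 = T1 score), with equal SDs σ and correlation r, and let D = M1 − M0.

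- cov(outcome, D) = (b1 − b0)(1 − r)σ²
- var(D) = 2(1 − r)σ²
- slope on D = (b1 − b0)/2, for any r

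As a share of b1:

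- b0 = −b1 (change drives screening): 1.0
- b0 = −b1/2: 0.75
- b0 = 0 (follow-up level drives screening): 0.5
- b0 = +b1/2: 0.25

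With b0 = 0 and a T2/T1 SD ratio k, the share is (k² − rk)/(k² + 1 − 2rk). For k = 0.8, r = .7 this is .08/.52 = 0.15; for k = 1.2, r = .7 it is .60/.76 = 0.79.

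**3. Arm-to-mediator path.** Change-score variance is 2(1 − r); the variance adjusted for T1 is 1 − r². Their ratio is 2/(1 + r): 1.54, 1.33 and 1.18 at r = .3, .5 and .7. Randomisation keeps this path unbiased, but change scores estimate it less precisely.

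**4. Power with a binary outcome.** All inputs beyond the 115 per arm and the screening rates are assumptions. The arm effect is 0.4 SD (the ±1 reading of .2). The log-odds is 0.77 per SD, which is .39 on the latent standardised scale: 0.77/√(0.77² + 3.29) = .39. The correlation r is .3/.5/.7. A 95% Monte Carlo interval for the product of paths stands in for the percentile bootstrap. One run with 800 trials per cell (Monte Carlo SE at most √(.25/800) = 1.8 points) gave, in %, at r = .3/.5/.7:

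| Driver of screening | Slope, change only vs adjusted | 20% vs 5%: change only | 20% vs 5%: adjusted | 44% vs 20%: change only | 44% vs 20%: adjusted |
|---|---|---|---|---|---|
| Follow-up level (b0 = 0) | .36 vs .79 | 34/33/23 | 81/81/68 | 54/51/44 | 88/91/92 |
| Intermediate (b0 = −b1/2) | .58 vs .80 | 60/61/51 | 79/80/69 | 73–80 (separate run) | not tabulated |
| Change (b0 = −b1) | about .79 for both | 70/77/77 | 78/81/72 | 73/84/94 | 88/93/93 |

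In the level-driven row the indirect effect falls from 0.4 × .79 = .32 to 0.4 × .36 = .14. The slope is slightly under half because a logistic slope also shrinks when a predictor is omitted.

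Across repeat runs, level-driven power was 23–35% and 41–57% with change only, against 68–82% and 86–95% with adjustment. In the change-driven row the adjusted-minus-unadjusted differences are +8, +4, −5 and +15, +9, −1; repeat runs widen the extremes to about +17 and −6.

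**5. Linear-outcome check** (N = 230, .2 with ±1 coding, .39, percentile bootstrap). Level-driven: 57–65% change only, 88–98% adjusted. Change-driven: 73%, 84% and 97% change only, 87–98% adjusted.

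**The case against.** **The plan is silent; it does not refuse.** C.13 leaves the mediation models to be chosen appropriately, and a model of change that also conditions on baseline fits that wording. It also promises sensitivity analyses for all aims, and its covariates go beyond demographics. This stands: a reader might infer that the plan deliberately excludes baseline scores, and the documents do not support that. What remains is that no covariate rule names a baseline mediator score, so the text read literally gives a change-only model.

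**The halving is conditional.** This also stands. It needs follow-up level alone to drive screening and equal SDs. The documents give no b0, no SDs and no T1–T2 correlation. If change is the driver there is no attenuation.

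**Change scores are not the only threat to the 80%.** Correct. How .2 is scaled moves the plan's own figure from about 82% to 29% before any change score enters. The adjusted model still gives only about 68–70% for DVD versus usual care at r = .7. A separate logistic run with a log-odds of .706 (.39 × 1.81) left Sobel power at 57–66% after adjustment.

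**Adjustment has a price.** It does, but a small one: about 5–6 points when change is the driver, r = .7 and the contrast is 20% vs 5%. The adjusted slope was unbiased in every scenario tried; the change-only slope was unbiased in one.

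**Conclusion.** The point holds as a gap in the model specification, with a better model available at almost no cost. The change-only model is unbiased only when the baseline effect exactly cancels the follow-up effect, and the sponsor need not know which driver is true to prefer adjustment.

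The size is conditional. Under the inputs in step 4, change-only power is lower by roughly 35 to 50 points in the level-driven case, and the two models are similar in the change-driven case. Two stronger readings are tempting: that Aim 3 estimates will in fact be half their true size, and that adding the baseline score restores 80% power. The documents support neither. The first needs quantities they do not give. The second fails because the power statement has its own faults: "assuming the effect sizes from the intervention to mediator and from the mediator to outcome are moderate or higher" conflicts with a path called small, and the .39 is attached to the wrong pair of variables for a mediation calculation.

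**What to change.** 1. In C.13, Aim 3, write out both equations. Use the T2 score as mediator, with the T1 score of the same scale as a covariate in the mediator equation and in the logistic outcome equation. The plan may keep change as the mediator if T1 is in both: b1·M1 + b0·M0 = b1·D + (b0 + b1)·M0, so the mediator coefficient is the same. The T2 score without T1 is not a substitute: in the linear check with change as driver and r = .7, its bootstrap power was 33%.
2. In C.12, restate the mediation power for that model with a binary outcome, each contrast's screening rates, an alpha, the coding of arm, an explicit mediator-to-outcome path, and a range for the T1–T2 correlation. Reconcile the two descriptions of path size. If DVD versus usual care falls short of 80%, say so.

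The cost is wording and one simulation. Table 3 already collects every listed mediator at T1 and T2, so no participants or interviews are added. The downside is the small power loss noted above if change is the true driver and the correlation is high.
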